The US Food and Drug Administration approved Nepafenac ophthalmic suspension 0.1% (NEVANAC®) in 2005 and Nepafenac ophthalmic suspension 0.3% (ILVERO®) in 2005 from Alcon Laboratories, Fort Worth, Texas, USA. Both ophthalmic suspension concentrations received an indication for the treatment of pain and inflammation associated with cataract surgery.

NEVANAC® ophthalmic suspension was compared with its vehicle in two double-masked, randomized clinical trials in which patients were dosed three-times-daily beginning one day prior to cataract surgery, continued on the day of surgery and for the first two weeks of the postoperative period. Nepafenac 0.1% treated patients were less likely to have ocular pain and measurable signs of inflammation (cells and flare) in the early postoperative period through the end of treatment than those treated with its vehicle. For ocular pain, both studies had a significantly higher percentage of patients (approximately 80%) in the Nepafenac group reporting no ocular pain on the day following cataract surgery (Day 1) compared to those in the vehicle group (approximately 50%).

ILEVRO® ophthalmic suspension was compared with its vehicle in two double-masked, randomized clinical trials in which patients were dosed once a day beginning one day prior to cataract surgery, continued on the day of surgery and for the first two weeks of the postoperative period. Nepafenac 0.3% treated patients were less likely to have ocular pain and measurable signs of inflammation (aqueous cells and flare) in the early postoperative period through to the end of treatment than those treated with its vehicle. In the two studies, Nepafenac cleared inflammation at day 14 post operation in 65% and 61% of patients compared to 32% and 24% of patients on vehicle. Pain free rates in the Nepafenac group were 86% and 84% compared to 46% and 38% of patients on vehicle. The Day 14 results for reduction of both pain and inflammation were statistically significantly superior to the vehicle.

This study will enroll approximately 75 qualified subjects (75 eyes) who have given written consent, have met all study inclusion/exclusion criteria and are scheduled to undergo unilateral cataract surgery with the implantation of an intraocular lens (IOL) will be enrolled in to the study.

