6.1.7.4 Punctal Plug extruded after surgery

A study subject that has noticed a plug has been extruded or lost during the follow-up period after surgery should immediately contact the Investigator and/or his/her staff and return to the Investigator's office as soon as possible. The Investigator will discontinue the study subject from the study and place them on open-label post-op medication(s) deemed necessary for the patient's welfare by the Investigator.

For any study subject where the plug has been lost, the Investigator will retro-illuminate or palpate the canaliculi to confirm the plug has not migrated into the canal. Information regarding the loss of any plug must be recorded in the source documents, CRFs and Accountability Logs.

NOTE: If an extruded plug can be located by a study subject, the plug should be returned and collected by the Investigator and/or his/her staff. If the plug tears or has separated, report this as a technical complaint ([Section 8.6](#)). Retain the plug for accountability of investigational supplies.

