10.4 Description of Statistical Methods

10.4.1 General Approach

All statistical tests will be two-sided and interpreted at a 5% significance level. Descriptive statistics (i.e., mean, standard deviation, etc.) will be provided for all continuous variables and frequency distributions will be generated for all categorical variables collected in this study.

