10.4.3 Analysis of the Secondary Endpoint(s)

The secondary efficacy variable will be the severity of ocular inflammation (anterior chamber cells and flare) report at visit 4, 5, 6 and 7 (post-op days 3, 7 and 14). For analyses using the intent-to-treat (ITT) data set, all data from all subjects with at least one post-operative follow-up inflammation evaluation will be included. For the per protocol (PP) analyses dataset, data from subjects or visits with significant protocol deviations will be excluded.

Efficacy analysis of primary and secondary endpoints will be based on observed data only. In the case of a significant amount of missing data, Last Observation Carried Forward may be used for sensitivity analysis.

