10.5 Sample Size

Since this is a pilot study, no formal sample size estimation was performed.

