10.6.1 Enrollment/ Randomization/Masking Procedures

Randomization will be stratified (or balanced) by study center. Patients will be randomized in a ratio of 2:1, 2 active (N-PPDS) for each placebo (p-PPDS). Treatment assignments for this study have been randomized in blocks of three (each sequential group of three, two lines are active treatment, and one line is placebo treatment), 25 blocks total. Using a random number generator (JMP 10.0 statistical software), each block is assigned three randomized numbers. The dataset is then sorted by ascending order by block, by random number. By ascending order, each line is assigned a subject number (e.g. 101-175). As a subject qualifies for enrollment, they will be sequentially assigned a subject number. The subject numbers designated what treatment group the subject will be assigned.

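### The only planned missing-data check is an optional LOCF with no trigger and no stated source visits; its bias can run either way, so it cannot show that the result is robust

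*Combined protocol and SAP*

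**What the plan says.** The missing-data rule closes Section 10.4.3 but covers both endpoints: "Efficacy analysis of primary and secondary endpoints will be based on observed data only". The next sentence is the only sensitivity analysis offered for missing data: "In the case of a significant amount of missing data, Last Observation Carried Forward may be used for sensitivity analysis". No amount is defined as significant, and no source visits are named. The per-protocol analysis in Sections 10.4.2 and 10.4.3 removes data; it does not test what was assumed about missing data.

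Several sections create early exits:

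- Section 5.5.1.1: termination, on the investigator's judgment, for moderate to severe pain or inflammation.
- Sections 5.5.1.2 and 6.1.7.4: discontinuation when the plug is lost after surgery, followed by open-label medication.
- Section 7.7.1: termination when an NSAID, corticosteroid or immunosuppressant is required, with follow-up through Day 14 or longer.

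Section 7.9.1 allows a rescue corticosteroid under stated criteria, also with follow-up. Sections 7.4.6 and 7.4.7 list a pain evaluation and a slit-lamp examination at early-exit and unscheduled visits. Section 10.4.2 defines the primary variable at Visits 4 to 7 only, and no section maps exit or unscheduled scores to those visits.

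**The concern.** A sensitivity analysis should move one stated assumption in a known direction, so that the reader can see whether the conclusion survives. LOCF assumes that the score would have stayed where it was at exit. After cataract surgery that is rarely plausible, because the endpoints are meant to change between Day 1 and Day 14.

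Two kinds of exit are foreseeable and LOCF treats them differently. A subject who loses the plug on Day 4 has early inflammation carried to Day 14 as a failure. A subject who leaves because of pain has either the failing score or an earlier no-pain score carried, depending on a rule that the plan does not give. With about 25 placebo subjects, five exits are 20% of the arm, so this choice could move the result noticeably.

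**Working it through.** The documents give no dropout rate, power or missing-data figure to reproduce. The inputs are the Day 14 rates in Section 2.1 and in the clinical studies table of Appendix 5. That table's first-study differences reproduce: pain 734/851 − 98/211 = 0.863 − 0.464 = 0.398 (stated as 40%); inflammation 552/851 − 67/211 = 0.649 − 0.318 = 0.331 (stated as 33%). Exit rates, Day 3 clearance and carried scores are assumptions.

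**1. Plug loss unrelated to outcome (inflammation, 65% v 32%).** The target is the Day 14 rate had the plug stayed in. Let p be the Day 14 clear rate, d the share lost after Day 3, and c the share clear at Day 3 (assumed 5% active, 3% placebo). Observed-only equals p in expectation, so the difference stays at 33 points. LOCF = p(1 − d) + dc.

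| Loss, active / placebo | LOCF active | LOCF placebo | Difference (points) |
|---|---|---|---|
| 20% / 20% | 0.65×0.8 + 0.2×0.05 = 0.530 | 0.32×0.8 + 0.2×0.03 = 0.262 | 26.8 |
| 20% / 10% | 0.530 | 0.32×0.9 + 0.1×0.03 = 0.291 | 23.9 |
| 10% / 10% | 0.65×0.9 + 0.1×0.05 = 0.590 | 0.291 | 29.9 |
| 10% / 20% | 0.590 | 0.262 | 32.8 |

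**2. Exits due to pain (86% v 46%).** Assume that 5% of active and 20% of placebo subjects exit, that none of them would have been pain-free at Day 14, and that a share g of exits has a no-pain score carried.

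- All randomized: 0.86 − 0.46 = 0.40.
- Observed-only: 0.86/0.95 − 0.46/0.80 = 0.905 − 0.575 = 0.330.
- LOCF: 0.40 + g(0.05 − 0.20) = 0.40 − 0.15g. This gives 40 points at g = 0 (failing exit score carried), 32.5 at g = 0.5, and 25 at g = 1 (prior no-pain score carried).
- LOCF is as diluted as observed-only when g = 0.0697/0.15 = 0.465.

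**3. Range over the exit rate.** Let a share f of Day 14 failures exit early, and let D be the all-randomized difference. Observed-only per arm = p/(1 − (1 − p)f). LOCF difference = D(1 − fg). Differences are in points.

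| Rates | f | Observed-only | LOCF, g = 0 | LOCF, g = 1 | g at which they match |
|---|---|---|---|---|---|
| 86 v 46 | 25% | 35.9 | 40 | 30 | 0.41 |
| 86 v 46 | 50% | 29.5 | 40 | 20 | 0.53 |
| 86 v 46 | 75% | 18.8 | 40 | 10 | 0.71 |
| 84 v 38 | 25% | 42.5 | 46 | 34.5 | 0.30 |
| 84 v 38 | 50% | 36.2 | 46 | 23 | 0.43 |
| 84 v 38 | 75% | 24.4 | 46 | 11.5 | 0.63 |

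**4. Mean pain score.** An illustrative simulation used 400,000 subjects per arm and a 0 to 5 score at Days 1, 3, 7 and 14, rounded from a normal variable with SD 1.1 and correlation 0.7 between adjacent visits. Subjects exit at the first score of 3 or more. All settings are assumed. The table shows the Day 14 difference, active minus placebo.

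| Course | Complete data | Observed-only | LOCF, exit score | LOCF, pre-exit score |
|---|---|---|---|---|
| Both arms resolving | −0.45 | −0.36 | −0.63 | −0.42 |
| Faster resolution | −0.15 | −0.11 | −0.34 | −0.15 |
| Placebo worsening | −0.96 | −0.78 | −1.06 | −0.86 |

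Observed-only understates the difference in each course. LOCF of the exit score overstates it. LOCF of the pre-exit score lies between slight to moderate dilution and almost no bias.

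**The case against.** The strongest reply is that the failing score would normally be the last observation. Sections 7.4.6 and 7.4.7 list pain and slit-lamp scores at early-exit and unscheduled visits, Section 5.5.1 asks for thorough reporting at the last visit, and Section 10.4.2 admits all data from subjects with one post-operative pain evaluation. On that reading, LOCF of the pain responder endpoint gives back the 40 points that observed-only loses. This stands as far as it goes. Carrying a pre-failure score is not the plan's stated rule. It arises only if LOCF is limited to Visits 4 to 7, as the endpoint definition allows, if the exit assessment is missed, or if a pain-free subject leaves because of inflammation. The plan rules out none of these.

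A reader might infer that LOCF errs in the same direction as the observed-data analysis and so gives false reassurance. The documents do not support that. In step 1 LOCF departs from an observed-data result that is unbiased. In steps 2 to 4, with exit scores carried, it moves away from a diluted one. The two analyses would then disagree.

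A reader might also infer that LOCF will be chosen after the results are known. Section 10.4.3 gives no timing, and Sections 10.3 and 10.6.3 place data verification and evaluability review before unmasking. Those steps do not cover this choice, however, and the interim analysis in Section 10.4.7 unmasks data after at least 25 subjects complete Visit 7. The timing is left open, and no more can be said.

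Two further points stand. Some rescued or terminated subjects are followed to Day 14, so their scores need not be missing. And the trial is a pilot ("Since this is a pilot study, no formal sample size estimation was performed"), so imputation models with about 25 placebo subjects must be very simple.

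**Conclusion.** The point holds in this form: the single missing-data check is optional, has no numeric trigger and no stated source visits, and its direction of error depends on exit reason and on which score is carried. In the plug-loss examples LOCF cuts a 33-point difference to 24 to 27 points when 20% of active subjects lose the plug, and by 3 points or less when 10% do. In the pain-exit example LOCF gives 25 to 40 points, against 33 for observed data and 40 for all randomized subjects. Neither agreement nor disagreement between the two analyses would show whether the conclusion is robust.

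The sizes rest on assumed exit rates, assumed Day 3 clearance and background rates from eye-drop trials. They show direction and scale; they do not forecast this trial. The label is cheap improvement: the main analysis is not shown to be wrong by this point, but a better check costs little.

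**What to change.** Delete the LOCF sentence and its trigger, and state that the following are always run:

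1. An analysis that counts exit for ocular pain or inflammation as non-response at later visits, with a written rule mapping early-exit and unscheduled scores to the analysis visits.
2. Multiple imputation by arm from earlier scores for exits unrelated to outcome (plug loss, missed visit, relocation), with a sparse model.
3. A tipping-point analysis that varies the imputed scores in each arm separately and reports where the conclusion changes.

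Sections 7.7.1 and 7.9.1 must be reconciled. One terminates a subject who needs a corticosteroid; the other permits a rescue corticosteroid with follow-up. Until they agree, it is unclear which later scores are missing, excluded, or observed under rescue. The SAP should then state how post-rescue scores enter the analysis.

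The cost is SAP wording and modest programming, with no new data. The drawback is that imputation will be imprecise with about 25 placebo subjects, so the models must stay simple.

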10.4.4 Safety Analyses

All study subjects who are exposed or deemed exposed to study medication will be evaluable for safety analysis. A subject is deemed exposed to study medication if they discontinue the study prior to surgery visit and were implanted with a masked PPDS.

The safety endpoints in this study are adverse events, visual acuity, slit-lamp parameters (Lid, conjunctiva, cornea), fundus findings, and use of rescue medication. Safety variables will be summarized using descriptive statistics.

The type, severity, duration and frequency of reported adverse events will be tabulated for each treatment group, by visit. Adverse events will also be summarized for events and a comparison of the proportion of study patients reporting adverse events between groups will be made using a chi-square test. Additionally, any adverse event experienced by a subject after signing informed consent and before exposure will be presented separately in the safety analysis.

Adverse events will be coded using the Medical Dictionary for Regulatory Activities (MedDRA). Treatment emergent AEs (those occurring after insertion of a study PPDS) will be summarized descriptively: The number and percentage of study subjects who experienced an AE and the total number of AEs will be summarized by system organ class and preferred term. Associated AEs, defined as AEs suspected to be treatment related by the investigator, SAEs and serious associated AEs will also be summarized, if necessary. Summaries of each type of event will be prepared by severity and for all severities combined.

Concomitant medication recorded and used during the study will be coded using the World Health Organization Drug Dictionary and listed by subject. Ocular concomitant medications will be identified by each eye in the listing.

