2.3 Potential Risks and Benefits

2.3.1 Known Potential Risks

A study subject randomized to receive N-PPDS may have unforeseen risk and could exhibit moderate to severe post-op inflammation and/or ocular pain. However, the risk associated with using N-PPDS to deliver a sustain release of Nepafenac are anticipated to be similar, if not less than, those of commercially available topical 0.1% and 0.3% ophthalmic suspension

of Nepafenac and silicone punctal plug products. In ocular surgery clinical studies with Nevanac®, adverse reactions that occurred in 5-15% of study patients included capsular opacity, decreased visual acuity, foreign body sensation, increase intraocular pressure, and sticky sensation. Adverse reactions that occurred in 1-5% of study patients included conjunctival edema, corneal edema, dry eye, lid margin crusting, ocular discomfort, ocular hyperemia, ocular pain, ocular pruritus, photophobia, tearing and vitreous detachment. Some of these reactions may have been the consequence of the surgical procedure. A summary of known potential risks to humans of topical 0.1% and 0.3% ophthalmic suspension of Nepafenac can be found in the NEVANAC® and ILEVRO® prescribing information (see [Appendices 4 and 5](#)).

A study subject randomized to receive a placebo Punctal Plug Delivery System (p-PPDS) could exhibit moderate to severe post-op inflammation and/or ocular pain. Other risks associated with using a p-PPDS are anticipated to be similar to commercially available punctal plugs use in humans. A study subject could experience ocular discomfort, epiphora, loss of plug, ocular inflammation, and subconjunctival hemorrhage. Less common, but serious, side effects are pyogenic granuloma, damage to the muscle at the opening of the punctum, canaliculitis, or migration of the plug into the canaliculus requiring irrigation or surgery.

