3 OBJECTIVES AND PURPOSE

To evaluate the safety and efficacy of N-PPDS in the treatment of post-operative ocular pain and inflammation associated with cataract surgery.

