4 STUDY DESIGN AND ENDPOINTS

4.1 Description of the Study Design

This is a Phase 2, multi-center, randomized, parallel-arm, double-masked, placebo-controlled study. One (1) to 2 days prior to their scheduled cataract surgery, each study subject will be randomized (2:1) in to one of two treatment groups:

Group A: A total of 50 study subjects (50 eyes) will have an N-PPDS inserted in the lower punctum of their scheduled surgical eye.

Group B: A total of 25 study subjects (25 eyes) will have a p-PPDS inserted in the lower punctum of their scheduled surgical eye.

All plugs will remain in the study subject's lower punctum for a period of 2 weeks following cataract surgery.

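### The only between-arm safety comparison is a chi-square p-value with no risk difference or interval, and at 50 v 25 it says little about moderate adverse-event excesses

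*Combined protocol and SAP*

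**What the plan says.** Safety stands beside efficacy in the study's single objective (section 3): "To evaluate the safety and efficacy of N-PPDS in the treatment of post-operative ocular pain and inflammation associated with cataract surgery".

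Section 10.4.4 names one between-arm safety comparison: "a comparison of the proportion of study patients reporting adverse events between groups will be made using a chi-square test". It does not say whether a continuity correction applies. Section 10.4.1 sets the reading rule: "All statistical tests will be two-sided and interpreted at a 5% significance level".

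The rest of the safety analysis is descriptive: "Safety variables will be summarized using descriptive statistics". That covers adverse events by group and visit, treatment-emergent events by system organ class and preferred term, severity breakdowns, visual acuity, slit-lamp and fundus findings, and rescue use.

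No section plans a between-arm risk difference, a confidence interval or a margin for any safety outcome. The only confidence intervals in the document are in the 0.3% product label reproduced as Appendix 5. Section 10.2 states hypotheses for pain and inflammation only. Section 10.5 says that no formal sample size estimation was done because this is a pilot.

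Section 4.1 gives the arm sizes: "Group A: A total of 50 study subjects (50 eyes) will have an N-PPDS inserted" and "Group B: A total of 25 study subjects (25 eyes) will have a p-PPDS inserted".

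**The concern.** A pilot's safety comparison is mainly an estimation problem: how large an excess of events on the active plug is compatible with the data? A p-value read against 5% does not answer that. With arms this small, a non-significant result is compatible both with no excess and with a sizeable one, and the p-value alone does not separate the two.

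At stake is what the report can say about safety. With the planned output, the single formal statement would be that the difference was, or was not, significant. With an interval, the report could state the largest excess that the data do not exclude. The data needed are already collected.

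**Working it through.** The plan states no power or detectable difference for safety, so there is no figure of its own to reproduce.

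**Inputs.** From the plan: 50 N-PPDS and 25 p-PPDS subjects (4.1), chi-square test (10.4.4), two-sided 5% (10.4.1). Assumed: the event rates. The plan gives no rate for any adverse event. The label rates in the appendices (about 5 to 10%) are for individual reactions, so a range of base rates is shown.

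**Step 1. Probability that the test misses a true difference.** For rates p_C (placebo) and p_T (N-PPDS), sum over all 26 x 51 possible outcomes:

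miss = 1 - sum of Bin(a; 25, p_C) x Bin(b; 50, p_T) over outcomes (a, b) with p ≤ 0.05.

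| Placebo v N-PPDS (assumed) | Uncorrected chi-square | Fisher's exact |
|---|---|---|
| 10% v 20% | 82% | 87% |
| 10% v 25% | 66% | 73% |
| 10% v 30% | 48% | 55% |
| 20% v 40% | 59% | 61% |
| 30% v 50% | 60% | 65% |
| 10% v 40% | 18% | 21% |

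With Yates' correction the 10% v 30% miss rate is 62%.

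**Step 2. Cross-check of 10% v 30% by the normal approximation.**
- Pooled rate = (25 x 0.10 + 50 x 0.30)/75 = 0.2333.
- Null SE = sqrt(0.2333 x 0.7667 x (1/25 + 1/50)) = 0.1036.
- Alternative SE = sqrt(0.10 x 0.90/25 + 0.30 x 0.70/50) = 0.0883.
- Power = Φ((0.20 - 1.96 x 0.1036)/0.0883) = Φ(-0.035) = 48.6%, a miss rate of 51%. This agrees with the exact result.

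**Step 3. What an interval would add.** Suppose 10/50 (20%) on N-PPDS and 3/25 (12%) on p-PPDS report an event; the difference is +8 points.
- Test: pooled rate 13/75 = 0.1733; SE = sqrt(0.1733 x 0.8267 x 0.06) = 0.0927; z = 0.08/0.0927 = 0.863; chi-square = 0.744; p = 0.39.
- Wilson 95% limits: 11.2% to 33.0% for 10/50; 4.2% to 30.0% for 3/25.
- Newcombe lower limit = 8 - sqrt((20 - 11.2)² + (30.0 - 12)²) = -12 points.
- Newcombe upper limit = 8 + sqrt((33.0 - 20)² + (12 - 4.2)²) = +23 points.

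The test reports no significant difference. The interval shows that an excess of up to 23 points is not excluded.

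**Step 4. Events not seen.** For zero events in 50 N-PPDS subjects, the upper limit of the exact two-sided 95% interval is 1 - 0.025^(1/50) = 7.1%.

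**Step 5. Sensitivity to the number exposed.** Discontinued and disqualified subjects are replaced (5.5.2.2, 5.5.2.3) and all exposed subjects enter the safety analysis (10.4.4), so the safety set could exceed 75. At 60 v 30, the normal-approximation power for 10% v 30% is 57%, which is still a miss rate of 43%.

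**The case against.** The strongest reply is that the plan never draws the bad inference. No section says that a non-significant adverse-event test will be read as safety, and there is no safety hypothesis or non-inferiority claim that would need a margin. The objective is to evaluate safety, and the by-arm tables in 10.4.4, with a masked Medical Monitor reviewing events (8.9), are a recognisable way to do that in a pilot. A reader could also compute the interval from the tabulated counts. Low power for adverse events is common to almost any trial of this size, and large excesses would usually be found. All of this stands, and it limits the point to a modest one. It does not explain why the one formal comparison should be a test without an estimate.

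Three stronger readings are tempting, and the documents do not support them.
- *That the plan treats non-significance as reassurance.* It does not say so.
- *That a null result would confirm the expectation in section 2.3.1 that N-PPDS risks* "are anticipated to be similar, if not less than, those of commercially available topical 0.1% and 0.3% ophthalmic suspension". That sentence compares N-PPDS with marketed nepafenac drops and silicone plugs. The planned test compares it with the placebo plug, so it does not test the comparison with the drops.
- *That the adverse-event p-value feeds the Phase 3 decision.* The Phase III trigger in section 8.8 is evidence of efficacy. Safety enters there only as evidence of its lack, and the interim analysis in 10.4.7 lists no adverse-event test.

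A reader might also infer that a non-significant result is always the likelier outcome. It is not: at 10% v 30% the uncorrected test rejects 52% of the time.

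**Conclusion.** The point holds as a modest improvement in analysis and reporting, not as a demonstrated error. The formal safety comparison is a p-value without an estimate, in a trial whose sole objective includes safety. For a 20-point rise from a base rate of 10 to 30%, the uncorrected test misses between 48% and 60% of the time; for a rise from 10% to 20% it misses 82%. It does detect a rise from 10% to 40% about 82% of the time.

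These figures rest on assumed event rates, on 50 v 25 evaluable subjects, and on the uncorrected chi-square. Fisher's test and, where computed, Yates' correction miss more often. The conclusion does not depend on one base rate. No larger sample is called for.

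**What to change.** In section 10.4.4:
- Report the N-PPDS minus p-PPDS risk difference with a two-sided 95% interval (Newcombe or exact, named in advance) for any adverse event, any ocular adverse event and rescue use.
- For events not seen in an arm, give the upper limit of the exact two-sided 95% interval.
- Keep the chi-square p-value as descriptive only, and add a sentence such as: *A non-significant difference will not be interpreted as evidence of comparable safety; the report will state the largest excess risk that the interval does not exclude.*

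The cost is a few sentences and a few lines of output, with no new data, subjects or visits. The downside is that the safety statement will look less favourable, because the intervals will be wide.

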2.1 Background Information

Punctal plugs are medical devices designed to block the drainage of tear fluid from the eye; several models are approved and commercially available. Punctal plugs are classified by the FDA as a Class II Pre-Amendment medical device. Furthermore, plugs are not identified as significant risk devices on the FDA Information Sheet titled “Significant Risk and Non-Significant Risk Medical Device Studies.”

Mati Therapeutics Inc. is the first to use punctal plugs as an anchoring device for a drug delivery platform. A drug-eluting core is inserted into Mati’s proprietary punctal plug (Evolute® PPDS), which allows medication to be continuously released into the tear film of the eye over a period of time. This platform has the potential to become a viable alternative to eye drop therapy and could address significant compliance issues that currently exist with patients who will not or cannot properly self-administer eye drop medications.

Cataract surgery is the most commonly performed surgery in the nation, with more than 3.5 million of these procedures done annually in the United States. Multiple studies have reported noncompliance and self-administration difficulties with topical medications among cataract surgery patients ([Kholdebarin 2008](#); [Winfield 1990](#)). A 2014 study showed that 92.6% of patients incorrectly administered topical medications after cataract surgery ([An 2014](#)).

Although recent advances in cataract extraction (CE) surgery have decreased the physical trauma associated with ocular surgery, disruption of the blood–aqueous barrier during surgery can lead to the release of inflammatory mediators, increasing the risk of secondary ocular complications. Favorable post-operative outcome depends on the proper use of topical medications to shorten the inflammatory response induced by cataract surgery. Untreated, post-operative inflammation can increase the risk of mild iritis with increased cells and flare in the anterior chamber (AC) and can interfere with the patient’s visual rehabilitation. In rare cases, inflammation can lead to complications such as cystoid macular edema, posterior capsule fibrosis, keratopathy, fibrin reaction, or chronic uveitis. Therefore, anti-inflammatory agents are routinely prescribed to resolve post-op signs and symptoms of cataract surgery more rapidly and to improve patient comfort.

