8 ASSESSMENT OF SAFETY

8.1 Safety Variables

Safety variable for this study include any reported AE after screening, visual acuity, slit lamp biomicroscopy finding, fundus examination findings, use of concomitant and/or rescue medications. To optimize consistency of AE reporting across centers, the study subject will be asked a standard question to elicit any AEs. At each study visit or telephone evaluation of the study subject, study personnel will ask the following question:

"Have you had any problems since your last visit?"

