8.6.4 Anticipated Adverse Events

The following is a list including, but not limited to, ocular adverse events that are anticipated. Any event that is unlikely but anticipated must have an adverse event form completed and reported to Mati Therapeutics Inc. (see [Section 8.7](#) for reporting details).

- Endophthalmitis/Intraocular infection
- Hypopyon
- IOL dislocation

- Cystoid macular edema
- Pupillary block
- Retinal detachment/tear
- Corneal edema
- Iritis
- Raised IOP requiring treatment
- Visual symptoms requiring lens removal
- Tilt and decentration requiring repositioning
- Residual refractive error resulting in a secondary intervention

NOTE: Wound burps during the first week postoperatively and suture removal are not considered adverse events for this study.

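### The between-arm AE test pools all AEs while the protocol contradicts itself on whether study-eye pain and inflammation count, so benefit can mask an excess of other AEs on N-PPDS

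*Combined protocol and SAP*

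**What the plan says.** Section 10.4.4 names one between-arm test for adverse events: "a comparison of the proportion of study patients reporting adverse events between groups will be made using a chi-square test". The test is not restricted by term, eye or relationship to treatment. Section 10.4.1 sets the level: "All statistical tests will be two-sided and interpreted at a 5% significance level". The other AE displays in 10.4.4 are descriptive, by system organ class, preferred term and severity.

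Four places bear on whether pain and inflammation in the study eye enter that proportion:

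- **Section 8.2.1** defines an AE as an unanticipated sign, symptom or disease.
- **Section 8.6.4** lists anticipated ocular adverse events, including iritis, and says: "Any event that is unlikely but anticipated must have an adverse event form completed and reported to Mati Therapeutics Inc". The only events it declares not to be AEs are wound burps in the first post-operative week and suture removal.
- **Section 8.7** collects all AEs whatever their severity or attribution.
- **Section 8.1** has staff ask at each visit: "Have you had any problems since your last visit".

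The same phenomena are efficacy outcomes. Section 10.4.2 makes severity of ocular pain the primary variable. Section 10.4.3 begins: "The secondary efficacy variable will be the severity of ocular inflammation (anterior chamber cells and flare". Section 2.1 says that untreated post-operative inflammation raises the risk of "mild iritis with increased cells and flare in the anterior chamber (AC", so it describes iritis through the signs that are scored for efficacy.

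**The concern.** An any-AE proportion is useful for safety when it counts harms. If part of what it counts is pain and inflammation that nepafenac is expected to reduce, it becomes a net figure: fewer efficacy failures on N-PPDS offset more of anything else. A non-significant or favourable chi-square could then be read as reassurance about drug-related harm when it partly restates efficacy. Safety is half of the objective in Section 3.

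The protocol does not settle how much of this will happen. Read by Section 8.2.1, expected post-operative pain falls outside the AE definition. Read by Section 8.6.4, being anticipated does not keep an event off the AE form. With up to three sites, practice may differ between them.

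**Working it through.** **No figure to reproduce.** Section 10.5 says that no formal sample size estimation was done, and no AE rate is given. What follows is an illustration.

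**Inputs from the documents**
- Arms of 50 (N-PPDS) and 25 (p-PPDS): Section 4.1. Two-sided 5%: Section 10.4.1.
- Inflammation not cleared at Day 14: 1 − 0.65 = 35% on nepafenac 0.3%, 1 − 0.32 = 68% on vehicle (Section 2.1; Appendix 5, Clinical Studies, Study 1).
- Pain on Day 1: 1 − 0.80 = 20% on nepafenac 0.1%, 1 − 0.50 = 50% on vehicle (Section 2.1).

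**Assumptions, not in the documents**
- Other AEs (neither pain nor inflammation): 30% on N-PPDS, 10% on p-PPDS.
- Share *r* of eyes with the efficacy finding that is also recorded as an AE: 0, 10%, 25%, 50%.
- Other AEs independent of the efficacy finding, and no continuity correction in the chi-square.

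**Formulas**
- P(any AE) = 1 − (1 − other) × (1 − r × efficacy finding).
- For *a* of 50 and *b* of 25 with an AE, X² = 75 × [a(25 − b) − b(50 − a)]² / [50 × 25 × (a + b) × (75 − a − b)].
- The chance of detecting the excess is the sum of the binomial probabilities of all (a, b) with X² > 3.841 and a higher proportion on N-PPDS.

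**Worked case: inflammation, r = 25%**
- N-PPDS: 1 − 0.70 × (1 − 0.25 × 0.35) = 1 − 0.70 × 0.9125 = 36.1%.
- p-PPDS: 1 − 0.90 × (1 − 0.25 × 0.68) = 1 − 0.90 × 0.83 = 25.3%.
- The true 20-point excess appears as 10.8 points.

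| Share recorded as AE | Any AE, inflammation | Chance of detecting excess | Any AE, pain | Chance of detecting excess |
|---|---|---|---|---|
| 0 | 30.0 v 10.0% | 52% | 30.0 v 10.0% | 52% |
| 10% | 32.5 v 16.1% | 32% | 31.4 v 14.5% | 35% |
| 25% | 36.1 v 25.3% | 15% | 33.5 v 21.3% | 18% |
| 50% | 42.3 v 40.6% | 4% | 37.0 v 32.5% | 6% |

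A larger assumed excess, 40% v 10%, is diluted in the same way. With pain, the chance falls from 82% to 68%, 47% and 21% at the same shares.

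**Which row is plausible?** Section 2.3.1 gives ocular pain as an adverse reaction in 1–5% of patients in the topical 0.1% studies, against about 20% with pain on Day 1 on that drug. That is 1/20 = 5% to 5/20 = 25%. It is only a rough pointer, because the two figures need not share a time window or a definition. It favours the upper rows of the table over the bottom one.

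**The case against.** A reader might infer more than the text supports. Four stronger readings fail.

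- **That pain is certain to be counted.** Section 8.2.1 confines AEs to the unanticipated, and Section 2.3.1 foresees moderate to severe pain and inflammation in both arms. A site could properly leave expected pain out. The text is contradictory, so double counting is possible but not settled.
- **That any eye with residual cells is an AE case.** Iritis is the investigator's diagnosis. Section 8.6.4 speaks of unlikely events and lists iritis beside endophthalmitis and retinal detachment. Section 2.1 treats it as something that inflammation can lead to. No cell or flare grade triggers an AE form. The 35% and 68% count every eye without complete clearing and are not iritis rates.
- **That harms of the plug itself would be hidden.** Both arms receive the same silicone plug and excipients (Section 6.1.2, Appendix 6). Such harms should be similar in the two arms and would not show as a between-arm excess under any AE definition. The concern is with drug-related events.
- **That the test is likely to declare N-PPDS safer when other AEs are equal.** With other AEs at 20% in both arms, the chance of a significant result favouring N-PPDS rises only from 2.8% to 4.8% if 10% of inflamed eyes are recorded. It reaches 63% only if all of them are.

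It is also true that the preferred-term tables would show iritis and eye pain separately, that lid, conjunctival, corneal, acuity and fundus findings are separate safety endpoints, and that no decision rule uses the p-value. Even undiluted, the test misses a 20-point excess 48% of the time.

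These points limit the weight of the finding but do not remove it. The only tested AE comparison can still mix benefit with harm, and the protocol does not say whether it will. Separate tables show the components but give no comparison free of the efficacy terms.

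**Conclusion.** The point holds as a gap in Section 10.4.4 joined to a contradiction between Sections 8.2.1 and 8.6.4. To the extent that study-eye pain and inflammation are recorded as AEs, a nepafenac benefit pulls the AE proportion on N-PPDS down relative to placebo and can mask an excess of other drug-related AEs.

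In the illustration, recording even a tenth of these findings takes the chance of detection from about one in two to about one in three. Recording half of them nearly removes it. The direction follows from the design if the plug works as hoped. The size rests on assumed other-AE rates, an assumed recorded share, independence, and efficacy rates carried over from topical nepafenac to the plug. The change is worth making because it is cheap and removes the ambiguity before any unmasking.

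**What to change.** 1. Reconcile Sections 8.2.1 and 8.6.4: state whether study-eye pain and anterior chamber inflammation scored as efficacy are also AEs, so that all sites record alike.
2. In Section 10.4.4, keep the all-AE chi-square and add the same comparison excluding a list of study-eye efficacy terms: ocular pain; iritis; anterior chamber cell, flare or inflammation. Tabulate the excluded terms by arm.
3. Fix the list before the interim unmasking in Section 10.4.7.

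AE collection and SAE reporting stay as they are. The cost is protocol wording, one extra table and early agreement on the list. The added comparison must supplement the all-AE comparison and not replace it: Section 2.3.1 names ocular pain as a nepafenac reaction and ocular inflammation as a plug risk, so a test without these terms could by itself hide harm from the product.
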